5 BASIC STUDY DESIGN

Vestibulodynia UPDATE is a multi-center, randomized, double-blind, placebo-controlled trial designed to determine the efficacy of peripheral lidocaine/estradiol cream, centrally-targeted nortriptyline pills, and combined treatments compared to matching placebo with the primary endpoints of change in pain, self-reported health, and cytokine/microRNA measures at 16 weeks and secondary endpoints of change in these measures at 8 weeks and 24 weeks.

5.1 Feasibility Study

An initial pilot study will be conducted for the baseline (0 week) visit to optimize and standardize performance of the clinical exam, measurement of PPTs, and collection and processing of blood and vaginal samples. We anticipate consenting 5 women at each study site for this feasibility study. These volunteers will be recruited via an email blast to the UNC and UCLA students and employees, and do not have to meet inclusion/exclusion criteria. Screening of eligible study

participants will not start until a review of the baseline data has been performed and there is a determination that the sites are performing the testing accurately.

5.2 Screening

Screening will be conducted in women aged 18-50 with symptoms of VBD. Informed consent will be obtained prior to the tampon test. Participants with a pain score of \geq “3” on a 0–10 numeric rating scale on the tampon insertion test will be eligible for enrollment. They will then complete the baseline evaluation measures and be randomized to one of four treatment arms. Women who have a pain score of 0-2 will be defined as a screen failure and will not be randomized.

5.3 Baseline Evaluation Phase and Randomization

Immediately following screening, research participants will complete all baseline assessments, including 1) completion of validated questionnaires to measure perceived pain, health, mood, and sexual function 2) vulvar exam and quantitative sensory testing to measure pressure pain thresholds at local (vaginal) and remote body sites, and 3) collection of biologic samples to measure local (vaginal) and systemic (blood) cytokines and miRNAs. The complete schedule of assessments to be obtained during the baseline visit is outlined in **Appendix A**.

Participants who fulfill all the inclusion criteria and none of the exclusion criteria will be randomly assigned on a 1:1:1:1 ratio to one of four treatment groups:

- 5% lidocaine/0.5mg/ml 0.07% estradiol compound vaginal cream + placebo pill
- placebo vaginal cream + nortriptyline pill
- 5% lidocaine/0.5mg/ml 0.07% estradiol compound vaginal cream + nortriptyline pill
- placebo vaginal cream + placebo pill

Medication assignments will be determined by the Duke Clinical Research Institute (DCRI) using randomized blocks, and then stratified by enrollment site. The DCRI will create a SAS program to generate the random sequence that will be loaded in RedCap. Participants and research personnel will be blinded to medication assignment.

[figure not shown]
During the baseline visit, participants will be counseled on optimal study medication administration. Participants will receive a written description of the study with contact numbers of study staff to present to their usual care provider(s).

5.4 Follow-up Phase

Randomized study participants will return to the clinic for their 8-, 16-, and 24-week follow up visits. The complete schedule of assessments to be obtained during the follow-up visits is outlined in **Appendix A**.

6 STUDY FLOW DIAGRAM

The study flow diagram below outlines the study procedures and assessments in chronological order.

7 STUDY POPULATION AND ELIGIBILITY CRITERIA

7.1 Study Population

The study population is women with VBD aged 18-50 of any race or ethnicity. Based on historical patterns of recruitment, we expect the racial distribution will be 65% White, 10% Asian, 10% Hispanic, 8% African-American, and 6.5% other groups. This distribution is quite similar to that among people reporting VBD in other U.S. demographic populations.

7.2 Inclusion Criteria

1. Female
2. Age 18-50 years
3. English-literate
4. Willingness to provide informed consent
5. Meeting criteria for diagnosis of VBD based on scoring a 3 or greater on a scale of 0-10 (with 0 being no pain and 10 being the worst pain imaginable) for either the
 - a. Tampon test
 - b. Pain with sexual contact involving penetration into the vagina
 - c. Pain with touch to the vaginal opening

7.3 Exclusion Criteria

1. Participants that will be enrolled in this study must be off medications for 30-90 days, depending on the medication dosage, frequency, duration, and half-life. All concomitant medications will need to be documented at the time of screening so the Principal Investigator and medical doctors at each participating site can determine a conservative window. Medications include, but are not limited to: topical lidocaine, estradiol, or lidocaine/estradiol to the vulvar vestibule, nortriptyline or other TCAs, pregabalin, and gabapentin.
2. Presence of active dermatologic vulvar disease or vaginal infection
3. Untreated atrophic vaginitis (participants may undergo treatment and re-evaluation for enrollment if the condition is resolved)
4. Previous vestibulectomy
5. Pregnant or planning on becoming pregnant during the study period.
6. Within the first six months of the postpartum period.
7. Currently breastfeeding/lactating, or within three months of discontinuing breastfeeding/lactation.
8. Active incarceration
9. Cancer within the past year.
10. Chemotherapy and/or radiation treatment within the past year.
11. Unstable medical condition (e.g., renal impairment, significant hematological disease, cardiovascular disease, hepatic insufficiency, neurological disorder, autoimmune disease, or respiratory illness)
12. Clear inflammatory states (e.g., morbid obesity)
13. Use of immunosuppressant medications
14. History of intolerance to nortriptyline, topical lidocaine, or topical estradiol
15. Contraindications to use of nortriptyline: current use, or use within the past 1-3 months, of MAOIs, some NDRIs, Ethylphenidate (DPH), MDPV (Methylenedioxypyrovalerone), Pipradrol (Meratran), Prolintane (Catovit/ Promotil); recent myocardial infarction, active psychotic or suicidal thoughts, narrow angle closure glaucoma
16. Contraindications to the use of lidocaine or local anesthetics
17. Contraindications to the use of topical estrogen therapy

18. Post-menopausal, defined as no menses for 12 consecutive months or surgical removal of both ovaries. (Hysterectomy is not an exclusion)
19. Have not had Botox of the pelvic floor muscles in the last 12 months, or pelvic nerve blocks in the last three months.
20. Are not currently enrolled or planning to enroll in another clinical trial during the course of this trial.
21. Are not currently receiving pelvic physical therapy

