Aching Pain	MPQ	1.14 (0.10)	1.23 (0.10)	2.06 (0.17)###	<0.0001
Tender Pain	MPQ	1.10 (0.06)	1.37 (0.13)	1.61 (0.16)**	0.003
Stabbing Pain	MPQ	1.00 (0.00)	1.13 (0.10)	1.39 (0.20)*	0.038
Unprovoked Genital Pain	GYN	0%	20%	30%	
Pain with 1 st Intercourse	GYN	N/A	67.5%	58.6%	
Pain with 1 st Tampon	GYN	N/A	51.3%	27.9%	

McGill Pain Questionnaire (MPQ), Gynecological Health Survey (GYN). MPQ data are Mean (SEM). *p<0.05, **p<0.01, ***p<0.001 vs HC. ###p<0.001 vs HC and VBD-p. GYN data are % women/ group.

Thus, qualitative and quantitative assessments of pain in the vaginal vestibule and remote body regions together with self-reported measures of perceived pain traits can distinguish women with VBD-p and VBD-c, and may be used to differentiate underlying mechanisms and indicate different pain management strategies.

3) VBD-p may be more effectively managed by peripheral therapy, while VBD-c may be more effectively managed by centrally-targeted or combined therapies. Treatment options for VBD include 1) non-medical interventions such as pelvic floor physical therapy and cognitive behavioral therapy, 2) topical medications (e.g., analgesic and hormone creams) applied to the vaginal vestibule, 3) centrally-targeted medications (e.g., tricyclics) taken orally, and 4) surgery.^{6, 10, 27} Surgical procedures such as vestibulectomy are high-risk and used as a last resort. Physical and psychological therapies are low-risk with published evidence, however are almost always used in combination with peripheral and/or centrally-targeted medications that have mixed results for successful pain management. A recent Cochrane review emphasized the need for randomized controlled trials to verify the efficacy of these commonly-prescribed medications, especially amongst different VBD subtypes.¹⁰

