8.9 Concomitant Medication

All research participants are not allowed to consume other topical lidocaine, estradiol, or lidocaine/estradiol medications, TCAs, MAOIs, SSRIs, SNRIs, or opiates throughout the entire course of the study. This will be confirmed by the research team at the 8-, 16-, and 24-week visits. Study team will discuss concomitant medication use at the baseline screening visit.

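### Exclusions 19-21 (and item 1 in part) are worded as conditions for entry, and sections 7.3 and 8.9 disagree on which co-treatments are restricted after randomisation

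*Combined protocol and SAP*

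**What the plan says.** Section 5.3 gives the operative rule: "Participants who fulfill all the inclusion criteria and none of the exclusion criteria will be randomly assigned on a 1:1:1:1 ratio". Most of the exclusion list in section 7.3 names the disqualifying condition itself; item 4, for example, reads "Previous vestibulectomy". Four items do not.

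- Item 19: "Have not had Botox of the pelvic floor muscles in the last 12 months, or pelvic nerve blocks in the last three months".
- Item 20: "Are not currently enrolled or planning to enroll in another clinical trial during the course of this trial".
- Item 21: "Are not currently receiving pelvic physical therapy".
- Item 1 opens as a requirement: "Participants that will be enrolled in this study must be off medications for 30-90 days". It goes on to name topical lidocaine and estradiol, tricyclics, pregabalin and gabapentin as examples.

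The inclusion list in section 7.2 does not restate any of these in the right direction.

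Section 8.9 sets what participants may not take after entry: other topical lidocaine or estradiol, and "lidocaine/estradiol medications, TCAs, MAOIs, SSRIs, SNRIs, or opiates throughout the entire course of the study". The team confirms this at the 8-, 16- and 24-week visits. Section 3.2 says of the non-drug options: "Physical and psychological therapies are low-risk with published evidence", and adds that they are nearly always combined with medications of the kinds under test.

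**The concern.** There are two separate faults.

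The first is one of direction. When a list is applied by the rule that a woman must meet none of it, an entry that describes the acceptable woman excludes her. A site that builds its eligibility form line by line from section 7.3 gets three questions whose expected answer runs against all the others.

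The second remains once the direction is put right. Sections 7.3 and 8.9 do not cover the same treatments. Several are restricted before randomisation and have no stated status afterwards. A woman turned away today for current physical therapy differs from a woman randomised today who starts it next week, yet nothing in the protocol addresses the second case. If such treatments are started during weeks 0 to 24, the trial has no scheduled record of the non-drug ones. Nobody could then say whether use differed between arms, or how far the week-16 tampon score reflects it.

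**Working it through.** **Direction of items 19-21.** No sample-size or power figure is involved, so the check is logical. Let B = recent pelvic floor Botox, N = recent pelvic nerve block, T = enrolled or planning to enrol in another trial, P = current pelvic physical therapy. Four yes/no features give 2 × 2 × 2 × 2 = 16 profiles.

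As printed, a woman meets item 19 if she has neither B nor N, item 20 if she lacks T, and item 21 if she lacks P. She escapes all three only if

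(B or N) and T and P.

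B or N holds in 3 of its 4 combinations, and T and P must each be present, so 3 × 1 × 1 = 3 profiles escape. The intended woman (none of the four) meets all three items and is barred. A woman with only one feature, say recent Botox, is also barred, because she still meets items 20 and 21.

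With the negation removed, she escapes only if she has none of B, N, T and P: 1 × 1 × 1 × 1 = 1 profile, the intended one. The two eligible sets have no profile in common.

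Item 1 is left out of this count because it mixes a requirement with a description of procedure. Its opening clause has the same fault.

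**Section 7.3 (read as intended) against section 8.9.**

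| Treatment | At entry (7.3) | During the study (8.9) |
|---|---|---|
| Topical lidocaine, estradiol | Item 1, washout | Barred |
| Nortriptyline, other tricyclics | Item 1, washout | Barred |
| Pregabalin, gabapentin | Item 1, washout | Not mentioned |
| Pelvic floor Botox | Item 19, 12 months | Not mentioned |
| Pelvic nerve blocks | Item 19, three months | Not mentioned |
| Pelvic physical therapy | Item 21, current | Not mentioned |

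Item 20 is not part of this mismatch. Another trial is not a therapy, and the item as intended already looks ahead to the course of the study.

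**Recording and analysis.** The Appendix A schedule has a medication-compliance row at weeks 8 and 16 but no row for physical therapy, Botox or nerve blocks after randomisation. The repeated-measures model in section 15.2 has no term or rule for added treatments. The closing paragraphs of section 15.4 analyse all randomised women as allocated.

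**The case against.** The case for leaving this alone has force on several counts.

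*The intent is plain.* Nobody would run a trial that admits only women with all the features it means to avoid, and sites probably read the items correctly. That stands. A reader might infer that the trial enrolled the opposite of its target population; the documents give no support for that. They also do not support saying that the text admits women with any one of the features, since only the combination escapes.

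*Analysis as allocated is a legitimate choice.* Under a treatment-policy approach, added therapy is part of the effect being estimated and not an error. That stands too, and is why the primary analysis need not change. It does not remove the need for a stated status and a record.

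*Co-treatment is partly checked.* Section 8.9 has its listed drugs confirmed at three visits, so the gap is narrower than a total absence of recording. The consent form and the content of the Appendix B handout were not available, so instructions given directly to participants could not be checked.

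*The effect on power is unknown.* A reader might infer a serious loss. The arithmetic for that, purely as illustration, starts from the 0.98-point difference in section 15.6, detectable with 80% power at alpha 0.0167. The implied standard error is 0.98/(2.394 + 0.842) = 0.303. Suppose an added therapy is worth 2 points and its use on placebo exceeds use on active treatment by 0, 10 or 20 percentage points. The difference becomes 0.98, 0.98 − 0.2 = 0.78, or 0.98 − 0.4 = 0.58, and power Φ(difference/0.303 − 2.394) is about 80%, 57% or 32%. If the true effect were 2 points, the same dilution leaves 1.8 or 1.6 and power above 99%. Neither input has a basis in the documents. The 2 points is the plan's clinically meaningful difference, not an estimate for any co-treatment; section 3.2 gives no effect size for physical therapy and reports a randomised trial in which gabapentin was ineffective for this condition. No uptake figures are given, and no difference between arms is as compatible with the text as 20 points.

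**Conclusion.** The point holds as a wording error in an operative eligibility rule, together with an unreconciled list of co-treatments. Items 19-21 cannot be applied as printed under section 5.3: they bar the intended profile and leave 3 of 16 unbarred, none of which is intended. Because the meaning is evident, this is a drafting fault whose likely harm is confined to forms copied from the text. The mismatch between sections 7.3 and 8.9 bears more on interpretation: five treatments restricted at entry (pelvic physical therapy, Botox, nerve blocks, pregabalin, gabapentin) have no stated status afterwards, and the first three have no scheduled record. Its effect on the treatment comparison cannot be sized from the documents and may be nil. The conclusion rests on the text alone and on no assumption about uptake or benefit.

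**What to change.** 1. Reword items 1 and 19-21 of section 7.3 as excluding conditions, or move them to section 7.2 as conditions for entry. Check any eligibility checklist and eCRF field derived from them.
2. Reconcile sections 7.3 and 8.9 so that each treatment restricted at entry has a stated status through week 24. Which status each should have is for the investigators to decide.
3. Record start dates of these treatments at the existing 8-, 16- and 24-week checks, and add the row to Appendix A.
4. Keep the intent-to-treat analysis as primary. Prespecify one supplementary analysis of the week-16 tampon score with a named strategy: for example, a hypothetical strategy that sets scores after the start of such a treatment to missing in the repeated-measures model. State that it relies on the model's ignorable-missingness assumption for those scores.

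The cost is protocol wording, a few extra fields at visits already planned, and one extra analysis.

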8 TREATMENT INTERVENTIONS

8.1 Interventions

Participants will be randomly assigned to one of four treatment groups: 1) peripheral treatment in the form of 5% lidocaine/0.5mg/ml 0.07% estradiol compound cream + placebo pill, 2) centrally-targeted treatment in the form of placebo cream + nortriptyline oral pill (up to 50 mg or highest tolerated dose), 3) combined treatment in the form of 5% lidocaine/0.5mg/ml 0.07% estradiol compound cream + nortriptyline; and 4) placebo cream + placebo pill.

Lidocaine/estradiol cream targets peripheral nerves and tissues affected in VBD; the comparison treatment will be an identical-appearing placebo Moisturel™ cream. Participants will be provided with a diagram and written instructions (see **Appendix B**), detailing how to apply the cream to the vaginal vestibule daily for weeks 1-16. Treatment with lidocaine/estradiol or placebo cream will be terminated at 16 weeks.

Nortriptyline is a centrally-acting tricyclic antidepressant that is FDA-approved for treatment of neuropathic pain. Dosing will begin with one 10 mg pill nightly for week 1, then two 10 mg pills nightly for week 2, three 10 mg pills nightly for week 3, four 10 mg pills nightly for week 4, and five for weeks 5 -16. In the event of side-effects without significant adverse events, participants will be advised to decrease dosage by one pill weekly until a tolerable dose is achieved. Treatment with nortriptyline or placebo pill will be tapered off over weeks 16-18, decreasing the dose by 10 mg every 4 days. Participants will be provided with a list of drugs to avoid that are known to interact with nortriptyline (see **Appendix C**).

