2 EXECUTIVE SUMMARY

Title	Vestibulodynia UPDATE: Vestibulodynia: Understanding Pathophysiology and Determining Appropriate Treatments
Indication	Three continuous months of insertional entryway dyspareunia and/or pain to touch/tampon insertion indicated by self-report as well as pain score of "3" or greater on the tampon test during screening.
Locations	Duke University, UNC, UCLA
Brief Rationale	Vestibulodynia (VBD) is a chronic pelvic pain condition that affects 1 in 6 reproductive aged women, yet remains ineffectively treated by standard trial-and-error approaches. Our group has identified two distinct VBD subtypes that may benefit from different types of treatment: VBD peripheral (VBD-p) subtype characterized by localized pain specific to the vulvar vestibule, and VBD central (VBD-c) subtype characterized by pain at both vaginal and remote body regions. Preliminary data further demonstrate that VBD-p and VBD-c subtypes differ with respect to patient reported outcomes (e.g., physical and mental health), production of cytokines (intracellular proteins that regulate the activity of pain nerves and inflammatory processes), and expression of microRNAs (small non-coding RNA molecules that regulate gene expression). Women with VBD-p exhibit normal psychological profiles; balanced circulating pro- and anti-inflammatory cytokines; and dysregulation in microRNAs that regulate the expression of genes in estrogen pathways. In contrast, women with VBD-c report decreased functional status and increased somatization; increased pro- but not anti-inflammatory cytokines; and dysregulation in microRNAs that regulate the expression of genes relevant to muscle, nerve, and immune cell function.
Study Design	Two-center, randomized, double-blind, placebo-controlled 2x2 factorial study enrolling 400 women to participate for 24-week duration.
Treatment	Participants will receive one of four treatments for 16 weeks: 
• 5% lidocaine/0.5mg/ml 0.07% estradiol compound vaginal cream + placebo pill• placebo vaginal cream + nortriptyline pill• 5% lidocaine/0.5mg/ml 0.07% estradiol compound vaginal cream + nortriptyline pill• placebo vaginal cream + placebo pill

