Local anesthetics and estrogen are among the most commonly prescribed peripheral treatments^{6,8,9} and tricyclic antidepressants are the most commonly prescribed centrally-targeted treatment.⁸ However, as concluded in a recent Cochrane systematic review, interpretation of treatment success remains difficult due to the limitations of published studies, including poor patient selection, lack of adequate controls, and limited follow-up data.¹⁰ Thus, there is a critical need for randomized controlled trials to evaluate the efficacy of these peripheral and centrally-targeted treatments, especially among women with different VBD subtypes. In response to RFA-HD- 18-480, we propose new multidisciplinary studies that will identify effective strategies for the management of two distinct VBD subtypes, while advancing our understanding of their different pathophysiologic mechanisms. We will compare the efficacy of peripheral, central, and combined treatments in alleviating objectively-measured pain and improving patient reported outcomes for women with VBD. In addition, we will evaluate cytokine and microRNA biomarkers that help determine underlying pathophysiology and predict treatment response. We will apply a randomized, double-blinded, placebo-controlled factorial study design to evaluate the analgesic efficacy of: 1) peripheral treatment with a 5% lidocaine/0.5 mg/ml 0.07% estradiol compound cream, 2) centrally-targeted treatment with the tricyclic nortriptyline 10 mg strength, or 3) combined peripheral and central treatment in women with newly diagnosed VBD. Women will be recruited from two study sites and complete a 4-month treatment phase, with outcome measures and biomarkers assessed at four time points (0, 2, 4, and 6 months). We hypothesize that women with VBD-p will exhibit increased levels of inflammatory mediators in the vaginal vestibule and preferentially respond to peripheral lidocaine/estradiol treatment, while women with VBD-c will exhibit increased levels of inflammatory mediators in blood and preferentially respond to centrally-targeted or combined treatment.

Our findings will 1) advance our knowledge of the pathophysiologic mechanisms underlying VBD-p and VBD-c, 2) determine the efficacy of peripheral, central, and combined therapies in alleviating pain in women with VBD-p and VBD-c, and 3) identify biomarkers that predict treatment response.

3.2 Scientific Premise for Aim 1

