8.2 Potential Side Effects and Risk Reduction Plan

Expected risks associated with lidocaine/estradiol compound cream include an adverse reaction to either medication or the compounded base. Lidocaine is well tolerated and safe, particularly with topical administration in small doses which significantly reduces the risk of lidocaine toxicity. The proposed daily dose is extremely small, with minimal systemic uptake when used as instructed. As with any medication, participants will be clearly instructed to use as directed. Significant over-usage would be required to approach toxicity. This is extremely rare in clinical practice. The medication will not be used in women with prior sensitivity or allergy to local anesthetics. A mild burning or tingling sensation with application is typical and resolves once the anesthetic takes effect. There is a rare risk of erythema, burning or blistering at the application site. The lidocaine will be compounded in a hydrophilic petrolatum, an inert and well-tolerated compounding cream. The second component of this compounded cream is estradiol. Like the lidocaine, women with prior sensitivity to this medication should not be enrolled, as well as women who have contraindications to topical estrogen therapy. The topical application has very low systemic uptake (0.01% per ½ gram dose), is well-tolerated and safe in reproductive-aged women. Women with potential contraindications to systemic estrogen, such as those with breast cancer, stroke or coronary artery disease, may still receive topical estrogen due to the extremely low absorption rate. In these cases, the treating physician will be contacted for permission to participate in the study, as is the protocol with clinical use of topical estrogen. Participants will be

instructed to notify the research team if they experience any adverse reaction.

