8.3 Drug Dispensing

Identical-appearing creams and pills will be packaged and distributed by Central Compounding Pharmacy to the UNC site, and by the Pacifica Compounding Pharmacy to the UCLA site. At the baseline visit, participants will receive a sufficient supply of study drug for weeks 1-8, and some (3 days) extra in the event of delay in scheduling visit 2. At the 8-week visit, participants will receive a sufficient supply of study drug for the remaining weeks 9-16, and some (3 days) extra in the event of delay in scheduling visit 3. Patients will be instructed to take the medication as required by the protocol.

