18.3.4 Summary of the Risks and Benefits

Risks.

Anticipated risks specific to this study are outlined in **Section 14.2** above.

Benefits.

Topical lidocaine and estradiol are used to manage pelvic pain disorders such as VBD, but are prescribed in the form of two separate creams. Compounding lidocaine and estradiol in the same cream would improve ease of use, promote more uniform distribution and absorption, and likely have added analgesic benefit. Additionally, the hydrophilic petrolatum is a nonirritating base that may be less likely to cause irritation compared to the typical ointment or jelly form of lidocaine. This compound improves ease of use and compliance. Nortriptyline is a tricyclic antidepressant medication that is FDA-approved to treat chronic neuropathic pain disorders (e.g., post-herpetic neuralgia). Nortriptyline is also a hypothesized treatment for VBD that is frequently prescribed to VBD participants and regularly used in the management of female pain syndromes such as VBD. When combined, the lidocaine/estradiol cream and nortriptyline therapies are theorized to have a synergistic effect. It is hoped that these interventions will provide a safe and effective therapeutic option for painful VBD. However, during the consent process, it will be stated that participants may experience no therapeutic benefit, but that their participation may inform additional research that helps others in the future. This research study has been designed to minimize the risks to participants. The risks in this study are reasonable in relation to the importance of knowledge gained as a result of this work.

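### The active cream's estradiol strength is stated as 0.5 mg/ml and as 0.07%, which do not agree; one strength with its basis is needed, confirmed by both pharmacies

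*Combined protocol and SAP*

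**What the plan says.** The estradiol strength appears in Section 2 (Executive Summary), Section 3.1, Section 5.3, Section 8.1 and Section 10.2. Each time it is a pair of figures for a single product:

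- Section 8.1: "peripheral treatment in the form of 5% lidocaine/0.5mg/ml 0.07% estradiol compound cream + placebo pill".
- Section 3.1: "peripheral treatment with a 5% lidocaine/0.5 mg/ml 0.07% estradiol compound cream".
- Section 2: "5% lidocaine/0.5mg/ml 0.07% estradiol compound vaginal cream + placebo pill".

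No section says whether the percentage is weight/volume (w/v) or weight/weight (w/w), gives a density, or says which figure governs.

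On supply, Section 8.3 has the creams and pills packaged and distributed "by Central Compounding Pharmacy to the UNC site, and by the Pacifica Compounding Pharmacy to the UCLA site". Section 10.2 repeats this, and Section 17.3.1 likewise assigns preparation of the investigational product to one pharmacy per site. The protocol describes no common formula and no check of potency across the two pharmacies.

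On the vehicle, Section 8.2 says of the active cream: "The lidocaine will be compounded in a hydrophilic petrolatum, an inert and well-tolerated compounding cream". Section 18.3.4 also names hydrophilic petrolatum as the base. For the placebo, Section 8.1 says "the comparison treatment will be an identical-appearing placebo Moisturel" cream.

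**The concern.** A strength written in two units should convert from one to the other, and this one does not under the ordinary w/v reading. The conflict sits inside the definition of the experimental product, so it carries into every arm that contains active cream. A pharmacist filling the order has to choose a figure, and two pharmacies make that choice separately.

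What is at stake is the meaning of the cream effect. If both pharmacies used the same figure, the trial result is sound but the protocol misdescribes the product. If they used different figures, the reported effect would be a mixture over two strengths, and the planned analysis would not reveal it.

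The vehicle raises a smaller question. The protocol names one base for the active cream and a different product for the placebo, and does not say whether the placebo is the active cream without its drugs.

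**Working it through.** **Inputs.** Strength: 0.5 mg/ml and 0.07% (Sections 2, 3.1, 5.3, 8.1, 10.2). Enrollment: 400 women, 200 per site (Section 9.2), allocated 1:1:1:1 (Section 5.3). Cream density: not in the documents; assumed range 0.80 to 1.10 g/ml, used only to test the w/w reading.

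**Step 1: w/v reading.** Percentage = (mg/ml ÷ 1000) × 100.

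- 0.5 ÷ 1000 × 100 = 0.05%. The plan's 0.07% is not reproduced.
- In reverse, 0.07% = 0.07 ÷ 100 × 1000 = 0.7 mg/ml.
- Ratio: 0.7 ÷ 0.5 = 1.40.

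**Step 2: w/w reading.** Percentage = (mg/ml ÷ (1000 × density)) × 100.

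- Density at which the figures agree: 0.5 ÷ 0.7 = 0.714 g/ml.
- At 0.80 g/ml, 0.5 mg/ml is 0.0625%; at 1.00, 0.05%; at 1.10, 0.0455%. It does not reach 0.07% anywhere in the assumed range.
- In reverse, 0.07% w/w is 0.56 mg/ml at 0.80 g/ml, 0.70 at 1.00 and 0.77 at 1.10. Against 0.5 mg/ml the ratio runs from 0.56 ÷ 0.5 = 1.12 to 0.77 ÷ 0.5 = 1.54.

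**Step 3: amount per application.** Section 8.2 mentions a half-gram dose. As w/w, 0.05% of 0.5 g is 250 micrograms of estradiol and 0.07% of 0.5 g is 350 micrograms. This shows the size of the conflict only.

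**Step 4: women affected.** Two of four arms contain active cream: 400 × 2/4 = 200, or 200 × 2/4 = 100 per site, each site's supply coming from its own pharmacy.

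**Step 5: what the analysis would do if strengths differed by site.** Randomization is stratified by site (Sections 5.3 and 8.7), so active and placebo are balanced within each site. Write D1 and D2 for the cream effect at the two sites. With equal sites, a model with one cream effect estimates about (D1 + D2) ÷ 2. The model for question 1a in Section 15.2 lists center as a main effect only. The model for question 1b adds terms in VBD subtype. Neither has a treatment-by-center term, so a difference between D1 and D2 would not appear. No sample size, power or alpha figure depends on any of this.

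**The case against.** The strongest reply is that nothing in the protocol shows a difference between sites. The same pair of figures is used everywhere, and no section gives one figure to one pharmacy and the other figure to the other. That stands. A reader might infer that strength is fully confounded with site, or that the trial cannot say what it tested. The documents do not support either reading: both need the pharmacies to have read the label differently, and compounding records would normally sit outside a public protocol. Sections 8.5 and 8.6 do require product accountability and pharmacy documentation, though they do not mention strength.

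It is also fair to say that stratification, with center in the model, protects the comparison with placebo even in the worst case. That stands too. What remains is the possible averaging in Step 5.

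Two figures side by side with no connecting word might be the remnant of an edit, with one meant to be deleted. This cannot be confirmed, and the pair is repeated in five sections. The correction would be the same.

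On the vehicle, a reader might infer that the active base is less irritating than the placebo, from Section 18.3.4: "the hydrophilic petrolatum is a nonirritating base that may be less likely to cause irritation". That sentence goes on to compare the base with the usual ointment or jelly forms of lidocaine, not with the placebo cream. The composition of Moisturel is not given, so neither a vehicle effect nor a loss of blinding can be shown. Section 8.2 also expects mild burning or tingling with lidocaine application, a cue that matching the base would not remove. The documents therefore do not show that the placebo needs to be remade.

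**Conclusion.** The conflict in the label is real and needs correcting. As w/v, the two strengths differ by a factor of 1.40. As w/w they agree only near 0.714 g/ml, a density the protocol does not state and one outside the assumed range of 0.80 to 1.10 g/ml. The label defines the product for about 200 women.

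The consequence for the trial is conditional. With a separate pharmacy at each site, different strengths are possible but not shown. If they occurred, the comparison with placebo would remain unbiased, while the cream effect would be an average over two strengths that the listed model could not detect.

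The two vehicle descriptions are a secondary query: the protocol names different products for active and placebo, and how far they differ cannot be judged from it.

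**What to change.** 1. Reconcile Sections 2, 3.1, 5.3, 8.1 and 10.2 to one estradiol strength, with its units and its basis (w/v or w/w). Which strength is right is for the sponsor to establish; no view is taken here.
2. Obtain confirmation that both compounding pharmacies work from that same specification.
3. Record the strength that any batches already made actually contain, by pharmacy.
4. As a query, reconcile the vehicle descriptions in Sections 8.1, 8.2 and 18.3.4, and state whether the placebo is the active cream's own vehicle.

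The cost is a protocol correction, a written confirmation from each pharmacy and a check of batch records. No change to the design, sample size or analysis model is required for this.
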